In addition to the primary sensitivity/specificity calculations, sensitivity/specificity and associated 95% confidence intervals will be calculated in predefined subgroups: sex, ethnic subgroups, rural and urban location, and educational status. As part of secondary analyses, receiver operating characteristic (ROC) curve analyses will evaluate different thresholds of the CAPTURE questionnaire score in defining a positive clinically significant + COPD screen, separately and in combination with low PEF characteristics, **and the additional CAPTURE questions**. As part of this exploration, participant and practice level data as well as interactions with the CAPTURE tool results, will be considered as predictors of clinically significant COPD using multivariable logistic regression. Corresponding positive and negative predictive values will be estimated across the range of prevalence percentages seen at the enrolled practices. Model selection in secondary logistic regression analyses will be based on forward selection using maximum likelihood theory, with entry into the model dependent on statistical significance at the 0.05 level. Exploration of this nature has the potential to produce artificially high operating characteristics (area under the curve [AUC], sensitivity and specificity) based on overfitting the data. SAS 9.4 PROC LOGISTIC includes a cross-validation approach to ROC curve analysis [ROCOPTIONS(CROSSVALIDATE)] that we will use when assessing operating characteristics for any new prediction tool that goes beyond the original CAPTURE metric considered in primary analyses. Once a final logistic regression model has been selected, classification thresholds for predicting clinically significant COPD will be described by the investigative team from the cross-validated ROC curve. Calibration plots of observed versus predicted sensitivity, and observed versus predicted specificity, will be conducted across previously specified subgroups of interest (sex, ethnic subgroups, rural and urban location, and educational status).

All of the above analyses will be applied to these additional populations: (1) patients with spirometrically defined COPD and (2) patients with mild COPD.

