Height and Weight: Height and weight will be recorded in order to determine appropriate prediction equations for spirometry and possible effect of obesity on spirometry. Height will be recorded in inches, and weight will be measured in pounds.

Demographic Data Collection: Demographic data including date of birth, gender, ethnicity, race, educational level, current employment status, living arrangement and health insurance will be entered into the EDC system.

Medical History: Previous medical diagnoses will include comorbidities such as cardiovascular, respiratory, and malignant disorders. Influenza vaccination history will also be recorded.

Statistical Analysis Plan

CAPTURE

Concomitant Medication Review: Respiratory medications will be recorded at baseline for all participants.

CAPTURE Additional Items Questionnaire: Participants will complete the 13 item self-administered questionnaire.

COPD Assessment Test (CAT): Participants will complete the eight item self-administered questionnaire. Each item is on a scale of 0-5 with higher scores indicating worse health status.

Respiratory Symptoms, Smoke Exposure and Exacerbation-Like Events: History of respiratory symptoms and exacerbation like events over the past year as well as smoke exposure (including e-cigarette or equivalent) will be recorded.

Adverse Events: Adverse events related to study procedures will be recorded by the coordinator.

Practice Characteristics: The locations of participating clinical practices will be categorized based on designation as rural by the Federal Office of Rural Health Policy (FORHP) / Health Resources & Services Administration (HRSA). A practice location will be classified as rural if the ZIP code appears in the Eligible ZIP Codes file downloadable from the FORHP website: <https://www.hrsa.gov/rural-health/about-us/definition/datafiles.html>. Other data describing the characteristics of participating practices will be collected from study site personnel.

6.6.2: Longitudinal follow-up

Follow-up efficacy assessments are collected from the time of baseline to 12 months in selected cohorts (as described in section 6.1).

Table 3: Data collected from medical records include:

| All participants undergoing 12-month follow-up as described in section 6.1 | Current Smokers Only |
|--|--|
| Clinical spirometry ordered or administered | Smoking cessation counseling |
| New recorded clinical diagnosis of COPD | New prescription for smoking cessation medication |

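### Cross-validating only the model that forward selection has already chosen leaves selection optimism in the reported accuracy of any new Aim 1 prediction tool

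*Protocol*

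**What the plan says.** Protocol 9.3.1 plans a secondary search for a better screen than the original CAPTURE rule.

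- Candidates: "participant and practice level data as well as interactions with the CAPTURE tool results, will be considered as predictors of clinically significant COPD". The ROC work also brings in the additional CAPTURE questions. SAP 7.6 gives their number: "Participants will complete the 13 item self-administered questionnaire".
- Selection: "Model selection in secondary logistic regression analyses will be based on forward selection using maximum likelihood theory". A term is added if its p-value is below 0.05.
- Recognised risk: "Exploration of this nature has the potential to produce artificially high operating characteristics".
- Remedy: "SAS 9.4 PROC LOGISTIC includes a cross-validation approach to ROC curve analysis", and this option is to be used for any tool beyond the original metric.
- Order of steps: "classification thresholds for predicting clinically significant COPD will be described by the investigative team from the cross-validated ROC curve". This comes only after the choice of terms is finished: "Once a final logistic regression model has been selected".

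Nothing says that selection is repeated inside the cross-validation. No bootstrap of the procedure, split sample or external validation is planned. SAP 4.1 places Aim 1 outside its scope, so the SAP adds nothing here. Protocol section 3 lists the AUC results for cut-points and for the best combination of patient and site characteristics as secondary endpoints, and 9.3.1 repeats the search for spirometric and mild COPD.

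**The concern.** Cross-validation protects against overfitting only for the steps that are redone without the left-out patient. Refitting coefficients removes the optimism from estimation. It does not undo the choice of terms, because a noise variable that passed p<0.05 did so partly on the strength of the patients who are later held out. The safeguard therefore covers only part of the risk that the protocol itself names. If a threshold is also chosen to look good on the same curve, that adds a further, separate optimism to sensitivity and specificity.

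At stake is the comparison that the secondary objectives invite: whether extra items, patient factors or practice factors improve on CAPTURE, and at what cut-off. That comparison would be tilted towards the extended tool.

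**Working it through.** **1. The plan's own precision figure.** For 500 cases and 90% sensitivity, 1.96 × √(0.90 × 0.10 / 500) = 1.96 × 0.01342 = 0.0263, which agrees with the ±2.6% in Protocol Table 9-1. All 21 cells of that table reproduce. The documents give no figure for optimism, so it was simulated.

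**2. Inputs.**
- Cases: 300–800 (Protocol 9.1.1.1). Confirmed non-cases: 3,400–4,400 (Table 9-3).
- Low-case scenario: SAP 13.1 reports about two spirometric COPD patients per practice, so 2 × 67 = 134 in 67 practices or 2 × 100 = 200 in 100. Clinically significant COPD is a subset of these. A count of 100 is an assumption within that limit.
- Candidate terms: not stated; 20, 40 and 80 assumed. As a rough guide, the 13 additional items plus the 35–39 category terms implied by the Aim 3 covariates in SAP 9.4 (its COPD cohorts left out) give 48–52 main effects before any interaction.
- Assumed: one CAPTURE-like score with AUC about 0.80 and independent normal predictors. The other candidates are pure noise, or include 10 weak true predictors (d = 0.15).

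**3. Expected false entries.** With k candidates including the score, about 0.05 × (k − 1) noise terms enter: 0.95, 1.95 and 3.95 for k = 20, 40 and 80. At 300 cases the simulated models held 2.0, 2.9 and 5.0 terms including the score, which agrees.

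**4. The procedure as worded.** Forward selection was run on all data, then leave-one-out AUC was taken for the selected model only and compared with the same model's AUC in 20,000 new patients. Residual optimism = cross-validated AUC − new-data AUC (60–150 replicates; differences taken before rounding).

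| Cases | Candidates | Apparent | Cross-validated | New data | Residual (SE) |
|---|---|---|---|---|---|
| 300 | 20 | 0.8017 | 0.7999 | 0.7986 | +0.0012 (0.0015) |
| 300 | 40 | 0.8022 | 0.7997 | 0.7961 | +0.0036 (0.0011) |
| 300 | 80 | 0.8099 | 0.8062 | 0.7921 | +0.0142 (0.0017) |
| 500 | 20 | 0.8026 | 0.8014 | 0.7990 | +0.0023 (0.0012) |
| 500 | 40 | 0.8037 | 0.8020 | 0.7972 | +0.0048 (0.0009) |
| 500 | 80 | 0.8031 | 0.8005 | 0.7944 | +0.0061 (0.0014) |
| 800 | 20 | 0.8015 | 0.8006 | 0.7983 | +0.0023 (0.0012) |
| 800 | 40 | 0.8021 | 0.8009 | 0.7982 | +0.0027 (0.0008) |
| 800 | 80 | 0.8051 | 0.8032 | 0.7960 | +0.0072 (0.0013) |
| 300 | 80 (10 weak) | 0.8264 | 0.8196 | 0.8038 | +0.0158 (0.0014) |
| 500 | 80 (10 weak) | 0.8223 | 0.8171 | 0.8088 | +0.0083 (0.0011) |
| 500 | 40 (10 weak) | 0.8193 | 0.8148 | 0.8123 | +0.0024 (0.0011) |
| 100 | 20 | 0.8044 | 0.7994 | 0.7950 | +0.0043 (0.0024) |
| 100 | 40 | 0.8109 | 0.8045 | 0.7897 | +0.0148 (0.0027) |
| 100 | 80 | 0.8202 | 0.8110 | 0.7821 | +0.0289 (0.0023) |

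With 40 or 80 noise candidates, 60–80% of the apparent optimism survives cross-validation (for example, 300 cases and 80 candidates: 0.0142 / 0.0179 = 79%). With 20 candidates the effect is near simulation error. With a single prespecified score there is none: −0.0004 (SE 0.0009) at 500 cases and −0.0068 (SE 0.0024) at 100. Selection is therefore the source.

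**5. Selection repeated inside 10 folds** (15 replicates each; nested / new data / as worded).
- 300 cases, 80 candidates (10 weak): 0.8077 / 0.8053 / 0.8222.
- 500 cases, 80 candidates (10 weak): 0.8073 / 0.8079 / 0.8159.
- 500 cases, 40 candidates (10 weak): 0.8115 / 0.8119 / 0.8161.
- 100 cases, 40 noise candidates: 0.7931 / 0.7927 / 0.8046.

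Three smaller runs (8 replicates; 40 noise candidates; 300, 500 and 800 cases) gave nested minus new data of −0.0036, −0.0030 and +0.0022. Nesting removes essentially all of the selection optimism.

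**6. Threshold.** If the threshold maximised sensitivity + specificity − 1 on the cross-validated curve, that index would be overstated at 300–800 cases by 0.015–0.030 with 40 candidates and about 0.025–0.045 with 80. At 500 cases about 0.014 arises from threshold choice alone, without any selection.

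**7. Against the score alone.** In a separate simulation with the score's AUC at 0.750, 100 cases and 60 noise terms, the cross-validated AUC was 0.759 and the new-data AUC 0.731. At 300–500 cases the gap was about 0.007–0.009. With 5 of 60 candidates truly predictive and 100 cases, the extended model beat the score in new data, 0.772 against 0.751.

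**The case against.** The protocol does not say outright that selection lies outside the cross-validation. It says that the option will be used when operating characteristics of a new tool are assessed. A nested procedure cannot be excluded. The sequence in the text makes the un-nested reading the likelier one, and if nesting is intended, a sentence would settle it.

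The size is small at the planned case count, and it depends on the base AUC. With a base AUC of 0.90 and 60 noise terms the gap was 0.013, 0.006 and 0.002 at 100, 300 and 500 cases. This stands: the effect matters mainly if cases are few or candidates many.

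A reader might infer that the extended tool would look better than CAPTURE while being worse. The documents do not support that as a general claim. It needs candidates of little true value and few cases, as in the 60-noise-term example. The protocol's background describes a systematic search for informative variables, so some candidates may carry real signal.

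A reader might also infer that thresholds will be chosen by maximising an index. The protocol says only that the investigators will describe them, so the threshold figures in the working are conditional on such a rule.

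Finally, this is exploratory work, and clinicians in the trial receive the original CAPTURE result, not a new tool. That limits the consequences but does not correct the reported accuracy.

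**Conclusion.** The concern holds in limited form. As worded, the planned cross-validation corrects coefficient fitting but leaves most of the selection optimism when many candidates carry no signal. Residual AUC optimism is about 0.001–0.016 at 300–800 cases and about 0.004–0.03 at roughly 100 cases. These figures rest on assumed candidate counts of 20–80, independent normal predictors and a base AUC near 0.80. The simulations did not model clustering by practice.

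It would be wrong to read this as a flaw in the primary Aim 1 result. That analysis applies a rule fixed in advance, with no selection. The point is worth a protocol clarification because it affects named secondary endpoints and the safeguard falls short of its stated purpose.

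**What to change.** State in Protocol 9.3.1 that the complete forward selection, and any data-driven threshold choice, is repeated within each cross-validation fold or bootstrap resample. Preferably leave out or resample whole practices: practice-level predictors are candidates, and leaving out one patient keeps others from the same practice in the fit. List the candidate terms and interactions beforehand, so that the extent of the search is known. Report the optimism-corrected AUC, sensitivity and specificity beside those of CAPTURE alone.

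If this is not done, label the new-tool results as exploratory and in need of external validation. The cost is protocol wording, more computing and slightly lower reported figures; no new data are needed.

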9.3.2 PRACTICE BEHAVIOR (AIM 3)

The primary analysis of the Aim 3 primary endpoint will be to compare the average cluster sample proportion (average proportion of CAPTURE+ patients per practice meeting composite endpoint) between intervention arms. Practices that do not identify any CAPTURE+ subjects will not contribute to the primary analysis. The primary analysis is a two-sample test comparing average cluster sample proportions that explicitly takes into account correlation between individuals treated within the same practice. A two-sided p-value < 0.05 will be considered statistically significant. This analysis corresponds to a generalized estimating equation (GEE) regression analysis with (1) individual-level binary composite outcome data, (2) CAPTURE intervention group as a covariate, (3) practice id used to identify correlated outcomes, (4) exchangeable correlation matrix that assumes similar correlation between all composite outcome results for patients within the same practice, and (5) an identity link function so that the coefficient parameter corresponding to CAPTURE intervention group represents a difference in outcome probability. The primary analysis would then correspond to a test for whether the CAPTURE intervention group parameter is non-zero. There are no planned interim analyses for the primary endpoint, the rationale being that this is not a pharmaceutical or device trial that would benefit from standard stopping rules for efficacy. A DSMB will be monitoring the study for safety and study integrity.

Secondary analyses on meeting the composite outcome for participants who are CAPTURE+ will employ the GEE analysis framework with individual and practice level predictors in addition to the CAPTURE intervention group. Interactions will be assessed. We will also use the GEE framework to study and describe each of the individual components of the composite outcome as they relate to individual and practice level outcomes. In the subset of smoking patients, we will use GEE regression analysis to study additional binary outcomes, such as incidence of physician counselling/recommendation to stop smoking, physician referral to a formal smoking cessation program, newly prescribed smoking cessation medication, and referral to a smoking quit line.

For each Aim 3 outcome that is collected via both medical record review and patient survey, the primary analysis will be among patients with complete outcome data from both the medical record and patient survey. Sensitivity analyses will be conducted by imputing missing outcome data using different assumptions and applying the primary analysis method to the resulting data sets. Sensitivity analyses will include (1) imputation of negative responses (i.e., responses indicating that the outcome has not occurred) for all missing patient survey responses, followed by analysis of all patients with medical record review data; (2) imputation of positive responses (i.e., responses indicating that the outcome has occurred) for all missing patient survey responses, followed by analysis of all patients with medical record review data; and (3) multiple imputation of all missing outcome data using the observed outcomes and covariates, followed by analysis of all patients selected for follow-up.

In participants who are CAPTURE+, change in CAT score will be analyzed using mixed models with a random effect for practice. The average cluster sample proportion of patients who experience exacerbations will be compared between intervention groups using methodology similar to that used for the primary endpoint. Subject to having sufficient mortality events, survival analysis allowing for correlation of endpoints within cluster (practice) will be used to compare mortality between

intervention groups and perform multivariable analysis. We will explore differences between intervention groups in the average cluster sample rate of hospitalizations again using GEE. All additional secondary analyses will also be applied to patients with clinically significant and spirometrically defined COPD, Mild COPD, PRISM, and symptomatic non-obstruction. Practices that do not have any patients with these conditions will not contribute to analyses of these secondary endpoints, respectively.

Model selection in GEE secondary analyses will be based on statistical significance at the 0.05 level using robust sandwich estimation of variability within clusters. Model fit will be checked by comparing observed versus predicted values within predefined subgroups of interest (sex, ethnic subgroups, rural and urban location, and educational status).

Analyses will be repeated in populations separated into cohorts based on enrollment date and the degree to which follow-up may have been affected by the SARS-CoV-2 pandemic.

9.3.3 CAPTURE IMPLEMENTATION RECOMMENDATIONS (AIM 2)

Site-specific practice information, clinician knowledge and behavioral questionnaires, as well as patient opinion survey responses are recorded primarily to populate focus group themes for qualitative analysis. Secondary analyses of individual clinician and patient response using frequencies, means, ranking and dispersion by clinician type, practice and PBRN is accomplished using SAS version 9.4. Correlation with implementation recommendation is determined using GEE variance models.

Audio transcripts of clinician focus groups will all be digital and entered into a qualitative data analysis program, NVivo for Mac. This program allows for an investigation of the salience, patterning, and contexts of key discourse items. Grounded theory methods will be used to identify and label recurrent themes and concepts within textual materials. Texts will be examined line-by-line, key phrases assigned tentative category labels, and coded passages grouped under the themes of feasibility, barrier and utility. The analyses will look for “traces” in dialogue, including repetitions, key words, evaluation statements, and metaphors. Micro-interlocutor analysis of focus group emergent themes, questions, answers and interactions will account for individual gaps in focus group participation. Change in salience, patterning, or content of key themes will provide further empirical evidence regarding the efficacy of our program’s efforts to impact clinician community norms and behaviors. An audit trail will be maintained to document the position of text material from which codes and themes are developed. We will use word/code counts of repetitive themes and concepts to indicate patterns. By allowing for open-ended responses, the narratives and notes will allow us to capture significant changes in participants’ attitudes or behaviors. Codes and themes will be discussed iteratively with the research team members to hone definitions and assure consistency of interpretation. We will establish a coding dictionary and all interviews will be coded using the complete set of themes. Reviewing the transcripts line-by-line, all substantive information will be assigned a priori codes as relevant for CAPTURE RE-AIM implementation planning, COPD diagnosis, CAPTURE intra-office clinical communication, and COPD and CAPTURE education preference, and COPD diagnosis quality improvement assessment. Two independent coders will code each document to assure inter-coder reliability. Preliminary results will be shared with the Aim 2 data team and will inform the development of the CAPTURE case studies and primary care practice implementation recommendations.

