| Description of Sites/Facilities Enrolling Participants: | 
Aims 1 and 3. Enrollment will occur in approximately 100 primary care practices affiliated with 7 primary care based practice networks (PBRN) across the United States who exhibit a broad range of gender, ethnic, racial, socioeconomic, and regional diversity.
 
Aim 2.
 
• Two primary care practices chosen by each of the same 5 PBRN co-investigator teams make up the 10 aim 2 practices from which clinician participants are enrolled. These 10 practices are separate from the 100 chosen practices in aims 1 and 3.• Patient participants are a sub-sample of those participants enrolled in aims 1 and 3. |
| Description of Study Intervention: | 
Aims 1 and 3. Primary care practices will be randomized to either receive basic COPD education and patient-level CAPTURE information with CAPTURE education (initially basic then later enhanced based on data collected in Aim 2) versus COPD education only.
 
Aim 2. Participating primary care clinicians from 10 varied practices are surveyed at three different time points and participate in two focus groups qualitatively assessing CAPTURE implementation strategy and COPD case finding approaches in primary care. Participating patients complete one 10-minute written opinion survey about CAPTURE.
 |
| Study Duration: | 
Aim 1 and 3. 4 years
 
Aim 2. 2 years
 |
| Participant Duration: | 
Aims 1 and 3. Up to 12 months
 
Aim 2.
 
• Primary care practice clinicians: questionnaires and focus groups (total 3 hours/participant) over 16 months.• Primary care patients: one 10-minute questionnaire/participant over 14 months. |

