5.2 EXCLUSION CRITERIA

Exclusion criteria for Aims 1 and 3

An individual who meets any of the following criteria will be excluded from participation in this study:

1. Previous clinician provided diagnosis of COPD
2. Treated respiratory infection (with antibiotics and/or systemic steroids) in the past 30 days of baseline
3. Participants unable to perform spirometry due to any of the following conditions within the past 30 days of baseline
 - a) Chest surgery
 - b) Abdominal surgery
 - c) Eye surgery
 - d) Heart attack
 - e) Stroke

Exclusion criteria for Aim 2

1. Clinician participants: current employment at practices participating in aims 1 and/or 3
2. Clinician participants: from practices providing fewer than 2 clinician participants
3. Patient participants: meeting the exclusion criteria for aims 1 and 3 (above)

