200 patient participants, 40 from each PBRN, are recruited as a sub-sample from Aim 1 practices. Patient participants fulfill all inclusion and exclusion criteria and receive informed consent for survey participation as part of aim 1.

Eligible participants complete a written one-time 5 to 10 minute CAPTURE opinion survey. Patient survey data is collected by Aim 1 research coordinators and is processed with Aim 1 baseline patient data. Patients receive a \$15 gift card for completion of the survey Aim 2 patient participation ends at the completion on the lone opinion survey.

Participants who prefer to complete the 5 to 10-minute survey online via Qualtrics will be sent a secure, Qualtrics link via email. The Qualtrics survey will include a brief, introductory screen affirming consent, describing the survey and instructions about participation. Once the survey is complete, participants will

see a screen with instructions about how to obtain their \$15 gift card and how to contact study staff with questions regarding the survey.

Modular online COPD education. Access to free, COPD on-line, continuing education is provided for all clinical staff at each practice. Each module will take 20 minutes or less. Modular components of and access to COPD education is described in the protocol. Aim 2 clinician participant access and completion of COPD education modules is assessed by clinician questionnaires and focus group item response over 12 months (between months 2 and 14 of Aim 2 timeline).

COPD in Primary Care/CAPTURE Introduction Focus Groups:

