From analyses of the 2 NPR and 2 PR CAPTURE Introduction focus groups per PBRN, baseline clinical staff questionnaire data, online CAPTURE opinion surveys, and on-site practice assessments, 1 primary care practice CAPTURE implementation case per PBRN (total implementation cases = 5) is created by the Aim 2 research team. Given local knowledge of chronic disease management quality improvement history, effort, challenge and successes, each PBRN's participation in case creation will be instrumental. The Aim 2 research team will lead case creation using evidence-based problem based learning (PBL) techniques (53-57). The Center for Research on Learning and Teaching (CRLT) at the University of Michigan will serve as research reference for PBL case development qualification (58). Each local PBRN PBL case will be distributed to the Aim 2 clinical staff at the 2 participating PBRN practices 2 weeks prior

to the CAPTURE Implementation focus groups, giving Aim 2 participants an opportunity to read the case introductions prior to the focus group session. Also, each practice will receive one additional non-PBRN case for focus group discussion as selected by the Aim 2 research team. Therein, each of the 5 CAPTURE implementation PBL cases will receive 2 comprehensive focus group reviews (see below).

CAPTURE Implementation PBL Case Presentation Focus Groups:

Each practice participates in a final pooled (NPRs and PRs together) on-site focus group. Two CAPTURE implementation cases (described above) are discussed at each focus group. The focus will explore, discuss, glean and create optimal 1) CAPTURE implementation, 2) CAPTURE clinical communication, 3) CAPTURE/COPD education and 4) CAPTURE primary care quality improvement recommendations pooled from all clinical practice levels for each of the 2 presented cases.

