9.2 POPULATIONS FOR ANALYSES

Aim 1

Population used for sensitivity calculations are all enrolled patients with clinically significant COPD as defined by post-bronchodilator $FEV_1/FVC < 0.70$ in addition to either ≥ 1 exacerbation-like event (ECOPD) within the past 12 months or an $FEV_1 < 60\%$ predicted.

Population used for specificity calculations are all enrolled patients with no demonstrable COPD as determined by research spirometry conducted upon study entry, $FEV_1/FVC \geq 0.70$.

Aim 2

Clinician participants: enrolled clinicians are from 2 primary care practices in each of five US PBRN regions that do not engage in Aims 1 or 3 investigation. Eligible clinicians include primary care providers and primary care clinical non-provider support personnel.

Patient participants: enrolled as a sub-sample of Aim 1 participants at baseline. One CAPTURE patient opinion survey is administered at baseline. Aim 2 participants fulfill the inclusion, exclusion and population analysis criteria of aim 1.

Aim 3

Populations used in 2-sample comparisons of outcomes between the two intervention arms will be based on randomization group (intent-to-treat analysis).

For primary analysis of each Aim 3 outcome, the analysis population will consist of all patients with follow-up data for that outcome from both the medical record review and the patient survey administered by the COPD Foundation (section 8.2).

Secondary analyses will be performed using alternative analysis populations, including

1. All patients with outcome data from the medical record review, and
2. All patients selected for follow-up.

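### Section 9.3.3 plans a GEE against implementation recommendations without defining it; patient answers, if included, link to recommendations only through five PBRNs, and clinician inference on ten practices needs a small-sample correction.

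*Protocol*

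**What the plan says.** Protocol section 9.3.3 first states the main purpose of the Aim 2 data: "patient opinion survey responses are recorded primarily to populate focus group themes for qualitative analysis". It then plans "Secondary analyses of individual clinician and patient response using frequencies, means, ranking and dispersion by clinician type, practice and PBRN", to be run in SAS. The next sentence is the whole specification of the inferential part: "Correlation with implementation recommendation is determined using GEE variance models". The SAP adds nothing, because its section 4.1 places Aims 1 and 2 out of scope.

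Four other places fix who is where:

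- Patients (section 8.3): "200 patient participants, 40 from each PBRN, are recruited as a sub-sample from Aim 1 practices".
- Aim 2 practices (synopsis, description of sites): "These 10 practices are separate from the 100 chosen practices in aims 1 and 3".
- The separation is enforced in section 5.2, which excludes "Clinician participants: current employment at practices participating in aims 1 and/or 3", and repeated in section 9.2: "enrolled clinicians are from 2 primary care practices in each of five US PBRN regions that do not engage in Aims 1 or 3 investigation".
- Recommendations: the Aim 2 primary endpoints are recommendations by clinicians. They are worked out in focus groups at the ten practices, ending with this step in section 8.3: "Each practice participates in a final pooled (NPRs and PRs together) on-site focus group".

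**The concern.** The correlation sentence has no subject of its own. It follows directly on a sentence about clinician and patient responses, and nothing limits it to clinicians. Read as written, patient answers are to be correlated with recommendations made in practices that none of those patients attend.

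Robust GEE standard errors rely on a large number of independent clusters. When the explanatory variable is constant within a cluster, the information on its coefficient comes from the number of clusters, not the number of people. Two hundred patients in five PBRNs, or up to 150 clinicians in ten practices, may look like a reasonable sample while supplying only five or ten independent values. At stake is a reported association between opinion and recommendation that reflects regional or practice differences and carries a standard error that is too small.

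**Working it through.** **Step 1. The plan's own numbers.** Patients: 5 PBRNs × 40 = 200. Clinicians: 10 practices × 15 = 150 at most. Total 200 + 150 = 350, which matches the synopsis. The documents give no power, alpha or sample-size figure for the GEE.

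**Step 2. What can be joined to what.**

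| Response | Where the respondents are | Where the recommendations arise | Shared unit |
|---|---|---|---|
| Patient survey | Aim 1 practices | Ten Aim 2 practices | PBRN only: 5 values, 0 shared practices |
| Clinician questionnaire | Ten Aim 2 practices | Same ten practices | Practice: 10 values |

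**Step 3. What few clusters allow.** With K cluster-level points, the smallest correlation significant at two-sided 5% is |r| = t / √(K − 2 + t²), where t is the 97.5% point on K − 2 degrees of freedom.

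- K = 5: t = 3.182, so |r| = 3.182 / √(3 + 10.13) = 0.878.
- K = 10: t = 2.306, so |r| = 2.306 / √(8 + 5.32) = 0.632.

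For an exact permutation test of a yes/no recommendation:

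- Five PBRNs split 2 versus 3: C(5,2) = 10 arrangements, smallest two-sided p = 1/10 = 0.10.
- Ten practices split 5 versus 5: C(10,5) = 252 arrangements, smallest two-sided p = 2/252 = 0.008.

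**Step 4. False-positive rate with no true association.** Assumptions, none of them in section 9.3.3: nominal two-sided 5% test, uncorrected sandwich variance, equal clusters, and a recommendation that takes one value per cluster. In the linear model the cluster mean of the responses has variance ICC + (1 − ICC)/n. The mean is regressed on the recommendation x, with Wald statistic |b| / √V, where V is the slope element of (X′X)⁻¹ (Σ xₖxₖ′eₖ²) (X′X)⁻¹. The test rejects above 1.96. There were 8,000 data sets per setting, with ICC 0.01, 0.05 and 0.15; ranges are over the three ICCs.

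| Clusters × size | Recommendation | Reject at 1.96 | Reject at t on K − 2 df |
|---|---|---|---|
| 5 × 40 (patients by PBRN) | binary | 24.1-25.2% | 9.8-10.4% |
| 5 × 40 | continuous | 33.9-34.4% | 17.5-18.2% |
| 10 × 15 (clinicians by practice) | binary | 10.8-12.5% | 6.6-7.8% |
| 10 × 15 | continuous | 17.9-18.6% | 12.9-13.5% |
| 100 × 5 (benchmark) | either | 5.3-6.2% | 5.0-5.9% |

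A logistic GEE with exchangeable correlation and a binary recommendation (600 data sets per setting, ICC 0.05 and 0.15) gave 23.8% and 25.5% with five clusters, and 11.0% and 7.7% with ten. Monte Carlo standard error near 25% is √(0.25 × 0.75 / 600) = 1.8 points for these runs and √(0.25 × 0.75 / 8,000) = 0.5 points for the linear ones.

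**Step 5. Other clusterings.** Clustering patients on their Aim 1 practice does not help, because the recommendation still varies only by PBRN. A separate simulation (1,000 data sets, four practices per PBRN, practice ICC 0.03) gave 14%, 22% and 31% for PBRN-level correlations of 0.02, 0.05 and 0.10. For clinicians in ten practices of unequal size (2 to 15), it gave 14-15%.

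**The case against.** The strongest reply is that section 9.3.3 does not say that patient answers are correlated with anything. The sentence names no variable, cluster, test or alpha, and a clinician-only reading fits. The 0.05 rule with robust variance stands in section 9.3.2, which concerns Aim 3. A reader might infer that the plan definitely tests patient answers and will report invalid p-values. The text supports only the conditional statement: if patient answers are included and tested in the usual way, the error rate is far above nominal.

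A reader might also infer that the clinician GEE is invalid because every recommendation is a group product with at most ten values. The documents do not establish that. In section 8.3 the first focus groups are held separately for prescribers and non-prescribers, and the final groups discuss two cases each. Clinicians answer questionnaires three times, and the planned micro-interlocutor coding follows individual contributions. Recommendations could therefore be coded below practice level, and GEE is then a natural tool. The 8-19% applies only where the recommendation is a practice-level value.

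A third tempting inference is that a spurious association would shape the enhanced CAPTURE education in Aim 3. Sections 4.2 and 6.1.1 feed Aim 2 recommendations and education preferences into Aim 3, but nothing routes a GEE result there.

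Finally, the PBRN label is not the only connection. Survey results are meant to inform the focus groups and the one-per-PBRN cases. This is a procedural link, not a second data key. It weakens the case for a test, since some association may be built in, and each practice also discusses a case from another PBRN, which blurs the regional match.

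What remains is that the natural reading includes patients, no practice contains both surveyed patients and recommending clinicians, and no small-sample method is named for either group.

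**Conclusion.** The point holds in conditional form. The separation of patients and recommending practices follows from the documents alone. Given that separation, a patient-to-recommendation model has five clusters and an uncorrected nominal 5% test has a true error rate of about 24-34%. A t reference with the usual sandwich still leaves about 10-18%. The five-cluster PBRN result hardly changes with ICC. For clinicians the link is sound, but with a practice-level recommendation the error rate is about 8-19%, depending on the model and on whether the recommendation is binary or continuous.

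The figures assume a 5% test and an uncorrected variance, neither of which section 9.3.3 states. The consequence is limited to a secondary analysis in a mainly qualitative aim; no Aim 1 or Aim 3 primary analysis is touched.

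**What to change.** Replace the correlation sentence in protocol section 9.3.3 with a specification that does the following:

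1. Limits the GEE to clinician responses, with practice as the cluster. It names the outcome, the predictor and how a recommendation is coded (per clinician, per staff group, per case or per practice).
2. Uses a small-sample-corrected sandwich variance together with a t reference. The t reference alone is not enough: in the table it leaves about 7-13% with ten practices. Where recommendations are coded per practice, a permutation test over the ten practices is the alternative.
3. Reports patient responses descriptively by PBRN only, with no correlation test against recommendations. The descriptive summaries by PBRN are already planned, so this removes a test and adds no work.

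The cost is wording; no new data are needed. Clinician intervals will be wider and the patient analysis becomes openly descriptive. With five PBRNs, nothing that could be tested reliably is lost. If the analysis has already been run, the same limits should be stated where it is reported.
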